NATIONAL POLYTECHNIC INSTITUTE

School of Medicine

SECTION OF GRADUATE STUDIES AND RESEARCH

“Gene modulation of NLRP3, IL-1 β and TNF- α in peripheral blood of patients with exogenous obesity treated with Berberine.”

Principal Clinical Research

PhD [name]
PhD [name]

Clinical sub-investigator

PhD [name]
Nutritionist [name]

ESM CE-01/7-12-2015

Mexico City, 15 August 2015

ABSTRACT

Background: In the treatment of exogenous obesity more than 800 traditional plants are used, such is the case of *Berberine* a phytopharmaceutical. This phytodrug has been shown to be anti-obesogenic in the Asian population, however its effect on our population is unknown. **Objective:** To determine the effects of *Berberine* on the gene modulation of NLRP3, IL-1 β and TNF- α in peripheral blood of patients with exogenous obesity. 120 patients were studied, treated with: hypocaloric nutritional plan, hypocaloric nutritional plan and moderate aerobic exercise, hypocaloric nutritional plan, moderate aerobic exercise plus *Berberine* and finally a normo-weight group without treatment. Anthropometric measurements, biochemical tests, clinical and gene expression data of NLRP3, IL-1 β and TNF- α were obtained. The anthropometric measurements, the treatment with *Berberina* obtained, with the exception of ICC, statistically significant results, while in the biochemical results the groups 2 and 3 showed similar results, those treated with Berberina only the VLDL

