In 2016 ENSANUT reported that the prevalence of overweight and obesity in women increased with respect to 2012, not only in adults but also in girls and adolescents, where the greatest increase was in rural areas. In the case of the combined prevalence of overweight/obesity in adults over 20 years of age, the data indicate that seven out of 10 adults suffer from this disease (72.5%), this percentage increased vs. 71.2% in 2012. The case of adult women was 75.6%, the increase was higher in rural areas (8.4%) vs. urban areas (1.6%). In men, the combined prevalence was 69.4%, with an increase of 10.5% vs. 2012^{19,20}.

When comparing the abdominal phenotype of obesity in adults >20 years of age was 76.6% with a higher prevalence in the female sex with 87.7% compared to 65.4% in men; the highest proportion of this disease is concentrated in groups from 40 to 79 years of age. In this category, the only significant percentage difference with the ENSANUT 2012 was 4.9 points in the case of the female sex. In other words, 72% of adults continue to be overweight or obese¹⁹. Therefore, there is concern that generations born in recent decades, because of diseases and health damage caused by obesity, may have lower longevity than previous generations¹³.

Figure 1: Comparison of the results of Prevalence of overweight and obesity in adult population in the ENSANUT, 2016.

[figure not shown]

Figure 2: Comparison of the results of Trend of abdominal obesity in adult population in the ENSANUT, 2016.

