What is the effect of Berberine on the gene expression of IL-1 β , TNF- α and NLRP3, in peripheral blood cells in individuals with exogenous obesity?

9. Objectives

General objective:

To determine the effects of Berberine on gene expression of cytokines IL-1 β , TNF- α and NLRP3 in individuals with exogenous obesity.

Specific Objectives:

1. To form groups diagnosed with exogenous obesity.
2. To evaluate anthropometric parameters
3. To evaluate biochemical parameters
4. To quantify the expression (mRNA) of NLRP3, IL-1 β and TNF- α
5. To establish the differences in gene expression between individuals with exogenous obesity and control subjects.

10. Hypothesis

Berberine inhibits gene expression of NLRP3, IL-1 β and TNF- α in individuals with exogenous obesity.

11. Material and methods

Type of study:

An experimental, analytical, longitudinal, prospective study of comparative groups was carried out.

Study subjects

Ninety patients with type I and II obesity will be selected, as well as 30 control subjects (healthy adults), who agreed to be donors of a peripheral blood sample, 2 tubes (1: biochemistry, 2: gene expression) channeled to the Obesity Program unit (Comprehensive Medical Service, ESM, IPN), with the following selection criteria.

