12.1. Selection criteria

Inclusion

Human peripheral blood obtained from adult donors with the following characteristics:

- Patients with $\text{BMI} \geq 30\text{kg/m}^2$
- With risk factors for type 2 diabetes (history of diabetic parents or siblings, sedentary habits)
- Fasting blood glucose $\leq 126 \text{ mg/dL}$ or glycosylated hemoglobin $< 6.5\%$
- Controlled arterial hypertension
- >18 years of age
- Accept and sign the informed consent

No inclusion

- Hypersensitivity to the components of the formula
- History of hypoglycemic episodes
- History of obesity of endogenous origin
- History of serious psychological, psychiatric, eating or neurological disorders

- History of hyperthyroidism, heart disease, diabetes, liver or kidney failure, glaucoma, epilepsy
- Pregnancy or lactation

Exclusion criteria

- Pregnancy
- Diabetics
- Presenting any serious adverse effect
- Patients who decide to withdraw from the protocol

Elimination

- Samples contaminated during processing
- Lysed blood samples
- Coagulated blood simple.

Variable Description

Independent Variable

Berberine

Category: quantitative.

Measurement scale: ratio.

Measurement unit: 500 mg with excipient q.s.

Operational definition: the tested dose of Berberine was 500 mg, given to patients for 3 months.

Dependent

Gene expression of IL-1 β , TNF- α and NLRP3.

Category: quantitative.

Measurement scale: discrete, continuous.

Measurement unit: arbitrary units.

Operational definition: Cytokines were determined with commercial qPCR equipment/reagents, and their arbitrary units/relative expression were determined by a specific standard curve for each one.

Observation method: open.

Sampling method: non-probabilistic sampling of consecutive comparative groups that met the selection criteria, until reaching the sample size that constituted the study groups (patients with exogenous obesity).

Operational description of the study: Berberine has been provided by the Medix laboratory, in 500 mg capsules, to treat patients for 3 months.

Study groups

The individuals will be distributed into four groups:

- Group 1. Individuals with exogenous obesity: nutritional plan intervention for lifestyle change.
- Group 2. Individuals with exogenous obesity: nutritional plan intervention, moderate controlled aerobic exercise for lifestyle change.

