- Group 3. Individuals with exogenous obesity: nutritional plan intervention, moderate aerobic exercise and Berberine phytopharmaceutical. With biweekly sessions for 3 months.
- Group 4. Normal-weight individuals without intervention.

Blood samples were taken after informed consent from the participants, they were informed of the intervention and the group to which they belonged, they were also taken at the end of the study.

Procedure

In the selection, obtaining information, anthropometry and blood biochemistry, the subjects of the study will be asked for authorization and their participation will be requested after a detailed explanation of the risks and benefits of the protocol, obtaining signed informed consent.

Obtaining the samples

The universe of the study will be individuals from 19 to 55 years of age with exogenous obesity; they will be recruited in the Obesity Projects area of the Postgraduate Studies and Research section of the Higher School of Medicine of the National Polytechnic Institute, referred by the Comprehensive Medical Service.

Each participant will be asked in writing to enter the study, each one was identified, and a clinical history was prepared with anthropometric measurements: weight, percentage of body fat, percentage of visceral fat, height, BMI. Peripheral blood will also be taken for blood biochemistry and messenger RNA extraction and qPCR tests to determine gene expression of NLRP3, IL-1 β and TNF- α .

Biochemical tests.

Peripheral blood samples will be evaluated by an external laboratory.

Blood samples will be collected at the beginning and three months after treatment. Participants were called at 7 am, after fasting for at least 8 hours, and the sample was collected in Vacutainer tubes (BD, USA), added with ethylenediaminetetraacetic acid (EDTA) to prevent coagulation. 4 mL of blood was taken from everyone; from there, 1 mL of Trizol (Sigma-Aldrich, USA) was added to 2 2 mL tubes with 100 μ L per tube. The blood was vortexed for 30 s and stored at -70 °C until processing. The rest of the blood was stored at -20 °C.

Anthropometric evaluation

The somatometry of each participant will be determined by wearing light clothing and without shoes: weight, height, % body fat, % visceral fat.

Height

It will be defined as the distance between the vertex and the support plane.

- Instrument: Stadiometer (Seca mod. 208).
- The measurement will be expressed in cm with a precision of 1 mm.

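### Normal-weight controls have no entry criteria they can meet, and the obese-versus-control comparison (specific objective 5) is neither matched nor adjusted for age and sex

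*Combined protocol and SAP*

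**What the plan says.** In section 11 (Material and methods, Study subjects), one sentence covers both populations. It begins "Ninety patients with type I and II obesity will be selected", continues "as well as 30 control subjects (healthy adults), who agreed to be donors of a peripheral blood sample", and ends "channeled to the Obesity Program unit (Comprehensive Medical Service, ESM, IPN), with the following selection criteria".

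The only inclusion list is in section 12.1. It is headed "Human peripheral blood obtained from adult donors with the following characteristics". Its items include a BMI of at least 30 kg/m², risk factors for type 2 diabetes (diabetic parents or siblings, sedentary habits), a limit on fasting glucose or glycosylated haemoglobin, controlled hypertension, and age over 18.

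Under Study groups, the comparator is "Group 4. Normal-weight individuals without intervention". Table 1 (section 2.4) puts normal weight at 18.50–24.99 kg/m². For people of short stature it classes a BMI from 23 to below 24.9 as overweight.

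Under Obtaining the samples, the 19–55 age range is given for people with exogenous obesity. Section 12.1 describes sampling as non-probabilistic and consecutive. The Statistical analysis section names ANOVA and Student's t test at 0.05, with no covariates.

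Specific objective 5 (section 9) is: "To establish the differences in gene expression between individuals with exogenous obesity and control subjects".

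**The concern.** There are two separate problems, and they should not be merged.

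The first is an eligibility contradiction. Read literally, the plan sends normal-weight controls to a list that requires obesity.

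The second is comparability. Objective 5 reads a difference in NLRP3, IL-1β and TNF-α expression as a difference between obese and non-obese people. That reading needs controls who resemble the patients on other determinants of expression, or an analysis that allows for the differences. The plan provides neither for age or sex. It also leaves open which patient sample is compared with the controls. Blood is taken at the start and at three months, and a post-treatment sample would mix obesity with the effects of the interventions.

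At stake is whether a result for a named objective can be attributed to obesity.

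**Working it through.** **Stated figure.** 90 patients + 30 controls = 120, which agrees with the Abstract ("120 patients were studied"). The documents give no effect size, SD or power, so 120 cannot be derived from design inputs.

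**Reading the criteria both ways.**

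- *The list covers everyone.* This follows from the Study subjects sentence and from the word for donors, which is used both there and in the heading of the list. BMI of at least 30 and BMI 18.50–24.99 do not overlap, so Group 4 cannot be enrolled as defined.
- *The list covers patients only.* The BMI item is worded for patients, which supports this. Controls are then defined only as healthy, adult and normal-weight. The 19–55 range is not stated for them. Patients are selected for diabetes risk factors and controls are not, so the groups differ by design on more than BMI.

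Under either reading, matching and stratification on age or sex appear nowhere, and no covariate is named in the analysis.

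**Illustration of size.** The documents give no age or sex distribution by group and no effect of either on these transcripts. The bias *b* below is an assumption, in SD units of expression, with the true obese–control difference set to zero. A bias of 0.10 SD would arise, for example, from a covariate correlated 0.2 with expression and imbalanced by 0.5 SD (0.2 × 0.5). A bias of 0.20 SD would arise from the same correlation with an imbalance of 1.0 SD (0.2 × 1.0).

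Formulas (normal approximation, two-sided 0.05; the protocol does not state sidedness):

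- SE = √(1/n₁ + 1/n₂)
- False-positive rate = P(Z > 1.96 − b/SE) + P(Z < −1.96 − b/SE)

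Standard errors:

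- 90 versus 30: √(1/90 + 1/30) = 0.211 SD
- 30 versus 30: √(1/30 + 1/30) = 0.258 SD

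The second row assumes the 90 patients are split equally over Groups 1 to 3; the protocol gives only the total.

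| Comparison | b = 0 | b = 0.10 SD | b = 0.20 SD |
|---|---|---|---|
| 90 v 30 | 5% | 7.6% | 15.8% |
| 30 v 30 | 5% | 6.7% | 12.1% |

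For scale, the difference detectable with 80% power is (1.96 + 0.84) × SE, about 0.59 SD at 90 versus 30 and 0.72 SD at 30 versus 30. A bias of 0.10 to 0.20 SD is well below that, but it still moves the error rate.

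**The case against.** The strongest reply is that this is loose wording. The BMI item is addressed to patients, the Study subjects sentence distinguishes patients from control subjects, and the sampling statement describes the study groups as patients with exogenous obesity. Controls are not wholly undefined: they are healthy adults of normal weight, and Table 1 gives the range. Nothing confines the No inclusion list, the minimum age or consent to patients. All of this stands, and a patient-only list is plausible. It removes the contradiction but not the missing age range, the one-sided selection for diabetes risk factors, or the unmatched and unadjusted comparison.

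A reader might infer several stronger claims that the documents do not support:

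- *That controls fail most of the list.* Only the BMI item is impossible for them. A healthy normal-weight adult can have a diabetic parent and sedentary habits, and the hypertension item can be read as a condition on those who have hypertension.
- *That the BMI contradiction itself confounds objective 5.* BMI defines the exposure. The confounding argument rests on age, sex and risk-factor selection.
- *That patients will be markedly older and more often female.* Section 2.3 does say "the highest proportion of this disease is concentrated in groups from 40 to 79 years of age", and gives 87.7% of women against 65.4% of men. Those are national figures for abdominal obesity, whereas this trial enrols by BMI with an upper age of 55. The combined overweight and obesity figures in the same section are closer, at 75.6% of women and 69.4% of men. With equal numbers of men and women (assumed), women would be 75.6/(75.6 + 69.4) = 52% of those affected and 24.4/(24.4 + 30.6) = 44% of the rest. This too is indirect evidence about who would enter the trial.
- *That Group 4 is the benchmark for whether treated patients return to normal expression.* The documents do not say so.

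**Conclusion.** The point holds in a limited form. The selection criteria and the definition of Group 4 must be reconciled, and specific objective 5 is exposed to uncontrolled confounding by age and sex under either reading of the list. To say that the comparison is confounded would go too far, because no baseline data by group are given. Neither the direction nor the size of any bias can be established from the documents.

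The false-positive rates of about 8–16% (90 versus 30) and 7–12% (30 versus 30) rest entirely on an assumed bias of 0.10 to 0.20 SD and, for the second pair, on an assumed equal split of patients. They show that a modest imbalance would matter, not that one will occur.

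The scope is objective 5 and any other contrast with Group 4. The research question, general objective and hypothesis concern berberine in obesity, and the contrasts among Groups 1 to 3 do not use the controls. The change should be made, but the berberine comparison does not depend on it.

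**What to change.** 1. Reconcile the Study subjects paragraph, section 12.1 and the Study groups and Obtaining the samples text by giving Group 4 its own criteria. These should be normal weight by Table 1 including its short-stature rule, the same 19–55 age range, and the shared glycaemia and No inclusion items as section 12.1 words them (the glycaemia item joins its two tests with *or*, and that should be kept). State whether the diabetes-risk item applies to controls, since adjusting for age and sex does not remove that difference.
2. If controls are still being recruited, frequency-match them to the patients on sex and age band.
3. In any case, analyse objective 5 with a linear model (ANCOVA) that includes age and sex, in place of the unadjusted tests.
4. State that objective 5 compares pre-treatment patient samples with the controls.

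The cost is slightly slower control recruitment and a little more analysis. No extra patients, tests or visits are needed. Age and sex are already entered for the body composition analyser. The Abstract reports results as if enrolment were complete. If it is, matching is no longer available, but steps 3 and 4 still are.

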12.1. Selection criteria

Inclusion

Human peripheral blood obtained from adult donors with the following characteristics:

- Patients with $\text{BMI} \geq 30\text{kg/m}^2$
- With risk factors for type 2 diabetes (history of diabetic parents or siblings, sedentary habits)
- Fasting blood glucose $\leq 126 \text{ mg/dL}$ or glycosylated hemoglobin $< 6.5\%$
- Controlled arterial hypertension
- >18 years of age
- Accept and sign the informed consent

No inclusion

- Hypersensitivity to the components of the formula
- History of hypoglycemic episodes
- History of obesity of endogenous origin
- History of serious psychological, psychiatric, eating or neurological disorders

- History of hyperthyroidism, heart disease, diabetes, liver or kidney failure, glaucoma, epilepsy
- Pregnancy or lactation

Exclusion criteria

- Pregnancy
- Diabetics
- Presenting any serious adverse effect
- Patients who decide to withdraw from the protocol

Elimination

- Samples contaminated during processing
- Lysed blood samples
- Coagulated blood simple.

Variable Description

Independent Variable

Berberine

Category: quantitative.

Measurement scale: ratio.

Measurement unit: 500 mg with excipient q.s.

Operational definition: the tested dose of Berberine was 500 mg, given to patients for 3 months.

Dependent

Gene expression of IL-1 β , TNF- α and NLRP3.

Category: quantitative.

Measurement scale: discrete, continuous.

Measurement unit: arbitrary units.

Operational definition: Cytokines were determined with commercial qPCR equipment/reagents, and their arbitrary units/relative expression were determined by a specific standard curve for each one.

Observation method: open.

Sampling method: non-probabilistic sampling of consecutive comparative groups that met the selection criteria, until reaching the sample size that constituted the study groups (patients with exogenous obesity).

Operational description of the study: Berberine has been provided by the Medix laboratory, in 500 mg capsules, to treat patients for 3 months.

Study groups

The individuals will be distributed into four groups:

- Group 1. Individuals with exogenous obesity: nutritional plan intervention for lifestyle change.
- Group 2. Individuals with exogenous obesity: nutritional plan intervention, moderate controlled aerobic exercise for lifestyle change.
- Group 3. Individuals with exogenous obesity: nutritional plan intervention, moderate aerobic exercise and Berberine phytopharmaceutical. With biweekly sessions for 3 months.
- Group 4. Normal-weight individuals without intervention.

Blood samples were taken after informed consent from the participants, they were informed of the intervention and the group to which they belonged, they were also taken at the end of the study.

Procedure

In the selection, obtaining information, anthropometry and blood biochemistry, the subjects of the study will be asked for authorization and their participation will be requested after a detailed explanation of the risks and benefits of the protocol, obtaining signed informed consent.

Obtaining the samples

The universe of the study will be individuals from 19 to 55 years of age with exogenous obesity; they will be recruited in the Obesity Projects area of the Postgraduate Studies and Research section of the Higher School of Medicine of the National Polytechnic Institute, referred by the Comprehensive Medical Service.

Each participant will be asked in writing to enter the study, each one was identified, and a clinical history was prepared with anthropometric measurements: weight, percentage of body fat, percentage of visceral fat, height, BMI. Peripheral blood will also be taken for blood biochemistry and messenger RNA extraction and qPCR tests to determine gene expression of NLRP3, IL-1 β and TNF- α .

Biochemical tests.

Peripheral blood samples will be evaluated by an external laboratory.

Blood samples will be collected at the beginning and three months after treatment. Participants were called at 7 am, after fasting for at least 8 hours, and the sample was collected in Vacutainer tubes (BD, USA), added with ethylenediaminetetraacetic acid (EDTA) to prevent coagulation. 4 mL of blood was taken from everyone; from there, 1 mL of Trizol (Sigma-Aldrich, USA) was added to 2 2 mL tubes with 100 μ L per tube. The blood was vortexed for 30 s and stored at -70 °C until processing. The rest of the blood was stored at -20 °C.

Anthropometric evaluation

The somatometry of each participant will be determined by wearing light clothing and without shoes: weight, height, % body fat, % visceral fat.

Height

It will be defined as the distance between the vertex and the support plane.

- Instrument: Stadiometer (Seca mod. 208).
- The measurement will be expressed in cm with a precision of 1 mm.

The subject stood up straight, with the heels together and supported on the back stop and so that the inner edge of the feet formed an angle of 60 degrees. The buttocks and the upper part of the back were in contact with the vertical table of the stadiometer. The subject was instructed to breathe deeply without getting up and maintaining the position of the head. The horizontal platform of the stadiometer was slowly lowered until it contacted the head of the subject, applying gentle pressure to minimize the effect of the hair and placing the head in the Frankfort plane.

Weight, % body fat and % visceral fat

- Instrument: Body composition analyzer (InBody770).
- The measurement will be expressed in Kg, with a precision of 0.1 kg.

It will be determined with the body analyzer, programmed with the required parameters (age, sex, height, among others). The subject stood in the center of the body analyzer platform, distributing the weight equally on both legs, without the body being in contact with anything around it, and placed his feet and hands on the equipment electrodes with his arms extended on both sides of the body, until the record was displayed on the screen and monitor.

Body Mass Index

The body mass index (BMI), also known as the Quetelet index, is an index of adiposity and obesity, as it is directly related to the percentage of body fat. The body mass index

was calculated by dividing the weight in kilograms by the square of the height in meters. This index has the advantage that its components (weight and height) can be easily measured. The nutritional status of participants was classified based on international anthropometric indicators, according to the WHO.

Nutritional Plan

There is no unanimity regarding the “ideal diet” because everyone has different anthropometry, blood biochemistry, clinical features, habits, economy, customs, pathologies, family/social interactions, which make standardization impossible. Therefore, based on the initial assessment, the following were prescribed:

“Classic” low-calorie diet: Recommended in most guides and consensus, it establishes a deficit of 500 to 1,000 calories per day, and a balanced distribution of nutrients: 45-55% carbohydrates, 15-25% protein, 25-35% total fat, and 20-40 g of fiber 1,⁴¹.

“Low-calorie” Mediterranean diet: This is the model supported by SEEDO because it represents this balanced and healthy approach, with a low intake of saturated and trans fatty acids and added sugars, and a high consumption of vegetable fiber and monounsaturated fatty acids. Its health benefits, including mortality, are clearly established in the literature.

High-protein diet: Based on the satiating effect and less loss of lean mass. The intake is increased to >1.2 g/kg/day, with a minimum intake of 90 g daily.

Nutritional Management

The nutritional management plan in this project will be aimed at improving the lifestyle and quality of life of patients, as well as reducing their body weight. This intervention will be done according to the nutritional management for obesity developed by nutritionists from INCMNSZ.

The goals of the nutritional plan were to establish healthy eating habits with a 10-15% reduction in body weight during treatment.

Nutritional Consultations

The consultations will be biweekly to evaluate body weight, anthropometry and adherence to the nutritional regimen, in addition to monitoring the modification of eating habits.

Clinical-nutritional history

In this clinical history, the lifestyle of the patients will be evaluated, the activities from the time they will wake up until bedtime will be questioned, their physical activities, allergies or intolerances, eating habits such as: meal times, tastes, preferences, quantities, type of food preparation, economic amount allocated, places of food, if they ate with electronic distractions, among others, to know the needs of each participant and adequately prescribe the food plan.

Food frequency

A food frequency survey from ENSANUT 2012 will be applied to learn about eating habits and determine the consumption of energy, important macro and micronutrients. The same survey analyzes and reports the results when capturing the data. With the evaluation of the diet and the anthropometric, biochemical, clinical, dietary and economic indicators, a nutritional diagnosis and the degree of obesity of each patient were established.

Energy expenditure

After the diagnosis, the prescription of the individualized food plan was prepared. The basal energy expenditure (BEE) was calculated with the Harris Benedict formula, and the current body weight.

While the total energy expenditure (TEE) was estimated from the physical activity of everyone by multiplying the BEE by the physical activity factor, according to the category of each one.

Energy prescription

A negative balance was induced to decrease 1kg of body weight per week, reducing from 500 to 1,000 Kcal per day. The caloric deficit was determined from the TEE for their current weight, the daily energy intake of the participants where the number of calories was calculated having the total energy expenditure minus 20% to obtain homogeneity in all participants.

Dietary distribution and composition.

The nutritional distribution with 50% carbohydrates was recommended, 10% simple carbohydrates, from fruit consumption, while the distribution with 30% fats was recommended, 10% saturated fats, and finally the distribution with 20% protein was half of animal origin and half of vegetable origin. The meal plans were adapted according to the requirements of each participant.

Each meal plan contained sample menus and an additional food exchange brochure, which contained the food groups and their equivalents, depending on whether the participants' weight decreased or the number of portions of each food group was maintained, as well as the calories of each nutritional plan.

The number of mealtimes was distributed in 5: 3 main meals (breakfast, lunch and dinner) and two additional snacks (morning and afternoon).

The lists of the Mexican System of Equivalents and the Institutional Program for the Prevention and Control of Diabetes Mellitus, IMSS, were used to prepare a list of portions

of the most consumed/common foods that were organized into food groups. The objective was to facilitate the participants' practice of new eating habits.

Anthropometric Evaluation

It allowed us to identify alterations in the nutritional status of each participant, as well as the associated risks; the anthropometric variables that were evaluated at the beginning of the program, every 15 days and at the end allowed us to assess the changes in the participants beyond weight loss, granting nutritional plans according to the specific needs for their anthropometric, biochemical, clinical, dietary, economic assessment and according to their family history.

Phytopharmaceutical

Therapeutic indications

A bottle of Berberine of 500 mg with excipient cbp of 102 tablets each was given, as well as a new bottle at each consultation and the participants handed over the empty bottles or with leftover pills. The way they should ingest them was 3 tablets: 3 times a day before each meal.

Treatment adherence log

The patients will give a treatment adherence log to indicate the day and time they took the tablets, as well as if they did not take them.

Adverse effects log

The patients will give a log in which they should indicate if they had any adverse events, to report them.

Controlled Aerobic Exercise

Controlled aerobic exercise on a treadmill, supervised by a sports physician, the frequency with which participants carried out their sessions was 3 times a week for 30 minutes each, at 60-70% of maximum heart rate. Due to the sedentary lifestyle of the patients, coupled

with obesity and its complications, an 'app' was installed on the participants' cell phones (with the exception of two: one did not have the device and one could not read or write, so they were provided with a semi-automated pedometer so that all participants had the same intervention), all were asked if they exercised, which was denied and their usual physical activity was minimal; in the initial phase of the protocol, their usual physical activity was determined (using the 'app'), which they were instructed to increase, with a goal of 10,000 steps or 150 min per week.

Gene expression

Extraction of total RNA

Blood samples will be lysed, and the material was extracted with TRIzol®Reagent, a mixture of guanidine isocyanate and phenol-chloroform, following the manufacturer's instructions. Once isolated, the total RNA will be suspended in RNase-free water to prevent its degradation and stored at -80°C. 140 µL of peripheral blood were used.

Extraction technique

Sample lysis will be carried out by adding one milliliter of TRIzol reagent and allowing it to incubate for 10 minutes.

1) Separation phase. Phenol-chloroform (0.2 mL per sample) was added, and the mixture was then centrifuged. Three phases were separated: a lower organic phase with the proteins, an interface with the DNA, and a transparent upper aqueous phase with the RNA. This fraction was transferred to a new tube to precipitate the RNA.

2) RNA precipitation by adding 0.5 mL of isopropyl alcohol. Centrifugation at 12,000g for 10 min at 4°C occurs, and the precipitated RNA forms a pellet or adheres to the walls and base of the tube.

3) RNA washing. This is done with 1 mL of 75% alcohol and centrifugation at 7500g for 5 minutes. The pellet is dried by vacuum centrifugation (spin vac pump) until the alcohol evaporates.

4) Re-suspension of total RNA. The samples are dissolved in RNase-free water, treated with 0.1% diethylpyrocarbonate (DEPC) (nuclease inhibitor). The integrity of the tRNA is checked on an agarose gel. Quantification of total extracted RNA

Sample concentration and purity will be measured by spectrophotometry (NanoDrop2000™, Thermo Fisher Scientific Inc., Waltham, Massachusetts, USA). Samples with a purity index (at 260/280nm) of 1.80-2.0 were considered adequate, indicating the absence of contamination.

Complementary DNA synthesis by reverse transcription

cDNA amplification will be performed using the “Transcriptor First Strand cDNA” kit for Rt-PCR from Roche (Roche Diagnostics GmbH, Mannheim, Germany), according to the manufacturer’s instructions. 500 µg of the cDNA sample was used in 20 µl volume. For the reaction, the following was done: The cDNA was synthesized from the tRNA of the samples and with the Invitrogen Roche kit (CA USA), in the following reaction mixture:

- 1) H₂O mili Q - 12.5 µL (the volume varies)
- 2) Buffer 10x MMLV – 2.5 µL
- 3) ‘Random primer’ - 0.5 µL
- 4) DTT 0.1 M—2.5 µL
- 5) dNTPs mix –1 µL
- 6) MMLV RT

The volume of the mixture is adjusted to 25 µL and the final product after the reaction in the conventional thermocycler (MasterCycler, Eppendorf) for 1 hour and stored at -20°C.

Real-time polymerase chain reaction, qRT-PCR

Procedure to determine the relative mRNA expression of genes of interest, using probes from the human transcriptome library (Roche, Library), LightCycler nano thermal cycler and TaqMan reaction mix (Roche Diagnostics). Oligosequences (sense and antisense) were

designed with ProbeFinder software version 2.45 (<http://www.universalprobelibrary.com>). The reaction mix was prepared according to the manufacturer's protocol with 5 μ l of cDNA of the appropriate dilution, in 10 μ l. The assay included a standard curve of 5 serial dilutions for each gene, and samples were normalized with the endogenous control β -actin. Each sample was performed in triplicate and data were analyzed with LightCycler nano software.

The thermocycler was programmed with the following scheme: preincubation for one cycle of 10 minutes at 95°C; the reaction for 45 consecutive cycles (denaturation at 95°C for 10 seconds, annealing at 60°C for 30 seconds and extension at 72°C for 1 second) and the final incubation at 40°C for 30 seconds.

Table 5. Oligonucleotide sequences used to determine gene expression.

Gen	Proteins	Sequences	Concentration
NLRP3	Proteína 3 que contiene dominios NACHT, LRR y PY	F: 5' GCA AGA CTT TGA CAA CAT GC3' R: 3'CAC CTG TTG TGC AAT CTG AAG5'	10nM
TNF- α	Factor de necrosis tumoral alfa	F: 5' CAGCCTCTCTCCCTTGAT3' R: 3'GCCAGAGGGCTGATTAGAGA5'	10nM
IL-1 β	Interleucina 1 beta	F: 5' TTG GGT AAT TTT TGG GAT CTT AC3' R: 3'CTG TCC TGC GTG TTG AAA GA5'	10nM
B-actina	Gen constitutivo	F: 5' AGC CAC ATC GCT CAG ACA C3' R: 3'GCC CAA TAC GAC CAA ATC C5'	10nM

Statistical analysis

The values of each determination are expressed as the mean \pm SE. The differences between the groups were calculated with ANOVA. Differences between the groups will be determined by using Student's T test. In all tests, a value less than or equal to 0.05 was considered significant.

Ethical aspects

The study will be of lower than minimum risk, since no blood was obtained from the participants in quantities greater than the limit established by the Regulations for Research on Human Beings of the General Health Law. The project was evaluated,

approved and accepted by the Research and Ethics Committee of the Higher School of Medicine of the National Polytechnic Institute.

The study was carried out in accordance with the ethical principles:

- Declaration of Helsinki of the WMA - Ethical principles for medical research involving human beings¹²⁶.
- Written and signed informed consent as stipulated in article 21 of the General Health Regulations on Health Research¹²⁷.
- As stipulated in article 17 of the General Health Regulations on Health Research, this project is classified as minimal risk¹²⁷.
- The protocol was carried out in compliance with the recommendations established in NOM-087-ECOL-SSA1-2002, which addresses matters related to Environmental Protection and Environmental Health; Biological-infectious Hazardous Waste¹²⁸.

Material Resources

